A Randomized Comparison of the *QuikClot® Radial® Pad* versus the Standard of Care TR Band® on Hemostasis after Transradial Artery Access (TRA)

Principal Investigator

[name]
Memorial Cardiac and Vascular Institute
[name]
[name]
[contact]

Funding Sponsor

Z-Medica, LLC

Study Product

QuikClot® Radial® Pad

510 (K) Number

K120782 (QuikClot® Interventional Hemostatic Bandage)
K152525 (TR Band Radial Compression Device)

Protocol Number

SAIRB-18-0021

Current Version Date

DEC 22, 2019

NCT number

NCT03535597

CONFIDENTIAL

This document is confidential and the property of Memorial Healthcare System. No part of it may be transmitted, reproduced, published, or used by other persons without prior written authorization from the study sponsor.

Study Summary

Title	A Randomized Comparison of the QuikClot® Radial® Pad versus the Standard of Care TR Band® on Hemostasis after Transradial Artery Access (TRA)
Short Title	QuikClot® Radial® pad on hemostasis after TRA
Protocol Number	SAIRB-18-0021
Methodology	Randomized, controlled, prospective study
Study Duration	1 year
Study Center(s)	Single center
Objectives	To evaluate the efficacy and safety of the QuikClot® Radial® pad on hemostasis after TRA, compared to the standard of care TR Band®, with the goal to hopefully develop a safe and efficacious technique to achieve more rapid patent hemostasis after TRA, and improve patient care by optimizing radial hemostasis management.
Number of Subjects	Consent up to 600 subjects with possible enrollment of 373
Diagnosis and Main Inclusion Criteria	Patients undergoing TRA for cardiac catheterization (CC) and/or percutaneous coronary intervention (PCI).
Study Product, Dose, Route, Regimen	The QuikClot® Radial® pad will be applied over the radial artery access site covered with either a Coban™ bandage or a TR Band® after TRA. Firm manual compression will then be applied over the QuikClot® Radial® pad after the sheath is removed for 5 minutes in the Coban™ cohort. The Coban™ cohort will then have the Coban™ bandage removed after an additional 25 minutes, then being covered with a Tegaderm™ dressing. In the QuikClot® Radial® pad combined with a TR Band® cohort, the radial sheath is removed and the TR Band® is inflated with 8 – 10 mL of air after a small amount of blood is noted on the QuikClot® Radial® pad. After 30 minutes the TR Band® is removed, leaving the QuikClot® pad covered with the Tegaderm™ dressing over the skin entrance site, to be removed the following morning.
Assigned Interventions	Consented subjects will be randomly assigned in the cardiac cath lab upon completion of their procedure into the following three arms: Arm 1 – Standard of Care with a TR Band® Arm 2 – QuikClot® Radial® pad combined with a Coban™ bandage Arm 3- QuikClot® Radial® pad combined with a TR Band®
Reference therapy	TR Band®

Table of Contents

1. Introduction	1
1.1 Background	1
1.2. Summarized Details of Investigational Products	2
1.2.1. Device Description	2
1.2.2. Intended Use	3
1.2.3. Technological Characteristics and Substantial Equivalence	3
1.3. Device Usage	3
1.4. Clinical Data to date	6
1.5. Dose Rationale and Risk/Benefits	10
1.6. Anticoagulation	11
2. Study Objectives	11
3. Study Design	11
3.1. General Design	11
3.2. Primary Study Endpoints	13
3.3. Secondary Study Endpoint	13
4. Subject Selection and Withdrawal	14
4.1. Inclusion Criteria	14
4.2. Exclusion Criteria	14
4.3. Subject Recruitment and Screening	15
4.4. Method for Assigning Subjects to Treatment Groups	15
4.5. Compliance Monitoring	15
5. Study Procedures	15
5.1. Visit 1 –At time of Standard of Care Cardiac Catheterization and/or PCI	15
5.2. Visit 2 – One day after enrollment	16
6. Safety and Adverse Events	16
6.1. Definitions	16
6.2. Adverse Event Reporting Period	17
6.3. Recording of Adverse Events	17
6.4. Reporting of Serious Adverse Events	17

7. Data Handling and Record Keeping.....	17
7.1. Confidentiality	17
7.2. Data Management.....	18
7.3. Sample Size and Statistics	18
7.4. Dissemination Plan.....	18
8. Ethical Considerations.....	18
9. References.....	19
10. Lists of abbreviations.....	21

1. Introduction

This document is a protocol for a prospective, randomized, open-labeled study to evaluate the safety and efficacy of the *QuikClot® Radial®* pad on hemostasis after TRA, compared to the standard of care device, the TR Band®, by assessment of patient tolerance of the device, local vascular complications, and the time taken to achieve hemostasis. This study is to be conducted according to US and international standards of Good Clinical Practice (FDA Title 21 part 812 and International Conference on Harmonization guidelines), applicable government regulations and Memorial Healthcare System research policies and procedures. Collection, recording, and reporting of data will be accurate and will ensure the privacy, health, and welfare of research subjects during and after the study.

1.1 Background

There is growing interest and increased use of the radial artery (RA) as the preferred access site for cardiac catheterization (CC) and/or percutaneous coronary intervention (PCI) due to its proven clinical benefits, including fewer access-site complications,¹⁻³ lower bleeding risks,^{4,5} shorter hospital stays,^{2,6} lower costs,^{2,7} and mortality benefits in ST-elevation myocardial infarction compared with the femoral artery (FA) approach.^{8,9} In addition, patients overwhelmingly prefer RA over FA access because of the increased comfort after the procedure.^{2,3,7}

Radial artery occlusion (RAO), however, is still an important complication seen in up to 8% of patients undergoing TRA.¹⁰⁻¹² RAO is known to be associated with use of large-size catheters, lack of procedural anticoagulation, and prolonged duration of radial compression after sheath removal.¹⁰⁻¹² Strategies such as higher dose of anticoagulation and shorter duration of hemostatic compression in conjunction with the patent hemostasis technique have been shown to reduce the incidence of RAO.¹⁰⁻¹² Several radial compression hemostatic devices have been introduced into clinical practice, with the aim of aiding radial access site hemostasis and limiting vascular complications.¹³ The most common compression device used in the United States is the TR Band® (Terumo, Japan), which is the standard of care device now being used to obtain radial artery hemostasis after TRA. This device wraps around the wrist and applies direct pressure to the radial arteriotomy site, typically for 2 to 3 hours after sheath removal, to achieve hemostasis. It is unclear, however, if using shorter compression times will further reduce the incidence of RAO without compromising hemostasis.

QuikClot® Radial® pad is a new hemostatic dressing that is composed of a kaolin-impregnated gauze. When kaolin contacts blood it immediately initiates the clotting cascade by activating Factor XII, resulting in shortened hemostasis times.¹⁴⁻¹⁶ Application of *QuikClot®* hemostatic pads over femoral artery access sites after PCI has been shown to reduce time to hemostasis with early ambulation.¹⁴ Recently, we applied the *QuikClot® Radial®* pad with an elastic adhesive bandage supplied by Z-Medica, LLC to achieve radial hemostasis after TRA with 5 minutes of manual compression followed by 25 or 55 minutes of elastic adhesive bandage compression in 20 patients. There was 100% successful hemostasis with the use of the *QuikClot® Radial®* pad in both groups with no rebleeding or increased complications noted when compared with the TR band®.¹⁵ Some subjects in this pilot trial complained about the supplied sticky elastic adhesive bandage, though. It was uncomfortable to remove because of the strong adhesive pulling their skin upon bandage removal. The operators also felt the elastic bandage was a bit complicated to apply. Because of this, we conducted another small pilot trial testing the feasibility and efficacy of using either a Coban™ bandage or Tegaderm™ dressing to secure the *QuikClot® Radial®* pad for achieving hemostasis post TRA, in hopes of improving patient comfort and satisfaction. The results showed that 5 minutes of initial manual

compression followed by 25 minutes of light compression with either a Coban™ bandage or Tegaderm™ dressing was successful in the 20 patients who underwent diagnostic cardiac catheterization and/or PCI, with 100% successful initial hemostasis without rebleeding, RAO, and other complications. This preliminary clinical evaluation suggested the *QuikClot® Radial®* pad combined with either a Coban™ bandage or Tegaderm™ dressing was an easy to use and effective hemostatic dressing that allowed for a short duration of compression and a painless hemostasis procedure without vascular or other complications noted.

We were encouraged by the performance of the *QuikClot® Radial®* pad in the above small pilot studies. The small sample sizes did not allow a definitive answer as to whether reduced compression times with the *QuikClot® Radial®* pad would reliably allow significantly shorter hemostasis times allowing for earlier discharge from the hospital, lead to less RAO post procedure, or improve patient comfort. We therefore designed the first version of this larger, adequately powered, prospective randomized trial to investigate the safety and efficacy of the *QuikClot® Radial®* pad combined with either a Coban™ bandage or Tegaderm™ dressing to achieve hemostasis following TRA, compared to the standard of care TR Band®. The *QuikClot® Radial®* pad will be applied over the radial artery access site using either a Coban™ bandage or only a Tegaderm™ dressing after TRA. Then, after sheath removal, firm manual compression will be applied over the *QuikClot® Radial®* pad covered by either the Coban™ bandage or the Tegaderm™ dressing for 5 minutes, followed by 25 minutes of light compression with the Coban™ dressing in the Coban™ cohort or 25 minutes of close observation after release of manual pressure in the Tegaderm™ only cohort.

After an interim analysis of 186 subjects, and a peer data safety and monitoring board (DSMB) committee review of the results, we elected to stop the Tegaderm™ only arm. With a failure to obtain initial hemostasis at 5 minutes in approximately 30% of the subjects in this arm of the protocol, we believed there would be little chance of this Tegaderm™ only protocol being adopted clinically. There were no safety issues with the Tegaderm™ only arm, as with repeated 5 minute manual compression cycles of the *QuikClot®* pad, hemostasis was obtained in all subjects. Mean hemostasis time in the Tegaderm™ only arm was 8.1 minutes. There was just clinical futility of this arm of the protocol as written, that was not detected in the small pilot trial performed using this protocol.

A new arm 3 will replace the Tegaderm™ only arm. This new arm 3 will use a *QuikClot® Radial®* Pad under a TR Band® with 30 minutes of compression. We have a large successful anecdotal experience of using a *QuikClot® Radial®* Pad under a TR Band® with 30 minutes of compression. We and others have demonstrated that use of a hemostatic pad under a TR band® significantly shortens hemostasis time, as compared to a TR band® alone, with no increased complications noted.^[17,18]

We will evaluate patient tolerance of the devices, local vascular complications, and the time taken to achieve hemostasis with the use of the *QuikClot® Radial®* pad and compare with the standard of care TR Band® on hemostasis after TRA. The results to be obtained will refine the *QuikClot® Radial®* pad use in the setting of hemostasis following transradial procedures, to hopefully develop a safe and efficacious strategy to achieve more rapid patent hemostasis following TRA, possibly lower RAO rates with shorter compression times, and improve patient care by optimizing radial hemostasis management.

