Our pilot study in 30 patients undergoing TRA demonstrated that application of the *QuikClot® Radial®* pad with 5 minutes of manual compression followed by a light compressive elastic bandage supplied by Z-Medica LLC for 25 minutes or 55 minutes achieved 100% hemostasis following TRA, with no increased complications noted (see Table below).¹⁵

Post-procedure outcomes with the use of QuikClot® Radial® pad

	TR Band® (n = 10)	QuikClot® 30 min. (n = 10)	QuikClot® 60 min. (n = 10)	P Value
Compression time (min)	149.4 ± 36.5	30.7 ± 2.2	60.9 ± 2.9	< 0.001
Initial hemostasis	5 (50%)	10 (100%)	10 (100%)	< 0.001
Pain scale	0	0	0	NS
Recovery unit time (min)	263.3 ± 56.3	238.9 ± 114.8	237.6 ± 71.6	NS
Access-site complications				
Radial artery occlusion	0 (%)	0 (0%)	0 (0%)	NS
Hematoma	0 (0%)	1 (10%)	0 (0%)	NS
Ecchymosis	0 (%)	0 (0%)	1 (10%)	NS
Edema	0 (%)	0 (0%)	0 (0%)	NS
Rebleeding	0 (%)	0 (0%)	0 (0%)	NS
Other	0 (0%)	0 (0%)	0 (0%)	NS

Results are mean ± standard deviation or n (%); NS, Not significant

Our recent other preliminary study (data not yet published) further demonstrated that application of the *QuikClot® Radial®* pad with 5 minutes of initial manual compression following by 25 minutes of light compression with either a Coban™ bandage or Tegaderm™ dressing was successful in all 20 patients who underwent diagnostic cardiac catheterization and/or PCI, with 100% hemostasis without rebleeding, RAO, and other complications. This preliminary clinical evaluation suggests that the *QuikClot® Radial®* pad combined with either a Coban™ bandage or Tegaderm™ dressing is an easy to use and an effective hemostatic dressing that allowed for a short duration of compression and a painless hemostasis procedure. Thus, there is a need to assess the true efficacy and safety of the *QuikClot® Radial®* pad combined with either a Coban™ bandage or Tegaderm™ dressing in the management of radial hemostasis following TRA in a larger number of patients.

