Although the TR Band® radial compression device has been used for years as the standard of care for hemostasis after TRA, there is no “standardized” compression/weaning technique. In a previous study, we used 40 minutes of compression with the TR Band® and then began weaning. 50% of subjects had to have air re-inflated upon the initial weaning of the TR Band®.¹⁵ Carrington reported that a 1-hour commencement of TR Band® weaning following TRA appears to be safe, with an 84% success rate.¹⁹ Because of this, the TR Band® in this study will be inflated for 60 minutes of compression without weaning, and then weaned over the next 60 minutes to hopefully achieve a high rate of hemostasis with a low rate RAO.

Potential risks may include: bleeding, pseudoaneurysm formation, hematoma, radial artery occlusion, local skin reaction (redness, swelling, and rash), pain, and numbness. Subjects may or may not have some or all of these risks from treatment with either one of the devices used in this study. The risks for the use of the *QuikClot® Radial®* pad are the same as for standard of care with TR Band®.

There may be an immediate potential benefit to patients. Application of the *QuikClot® Radial®* pad may shorten the time of compression compared with the standard of care TR Band®. Shorter radial artery compression times have been associated with less radial artery occlusion, thus potentially reducing the incidence of post-procedural radial artery occlusion. The light compression with either a Coban™ may help maintain patent hemostasis. Patient discomfort may also be reduced by shorter compression times and lower compression pressure.

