1.6. Anticoagulation

For diagnostic cardiac catheterization using TRA in this study, a heparin dose of 70 units/kg will be used, with a minimum of 4000 units and a maximum of 7000 units. For PCI, additional heparin to attain an ACT of > 250 – 300 seconds will be used, or bivalirudin at standard FDA approved doses described in the package insert may be used at the operator’s discretion. The option of continuing a heparin or bivalirudin infusion after the PCI will be at the operator’s discretion.

2. Study Objectives

The objective of this study is to evaluate the safety and efficacy of a kaolin-based *QuikClot® Radial®* pad combined

with either a Coban™ bandage or TR Band® to achieve hemostasis after TRA, compared with ‘standard of care’ mechanical compression with the TR Band®, with the aim to hopefully develop a safe and possibly superior hemostatic method after transradial access, thus improving patient care by optimizing radial hemostasis management.

3. Study Design

[figure not shown]

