7.3. Sample Size and Statistics

Based on the previous study¹⁷ on the use of TR Band® and our pilot study on the *QuikClot® Radial®* pad with either a Coban™ bandage or Tegaderm™ dressing for radial hemostasis, we anticipate an average initial successful hemostasis rate of 95% or higher in patients using the *QuikClot® Radial®* pad compression device, compared to an initial successful hemostasis rate of 84% in patients using the TR Band®, and no significant differences between the two *QuikClot® Radial®* pad arms. Using a type 1 error of 0.05 for each of the two comparisons of the *QuikClot® Radial®* pad with the TR Band® and power of 80% to detect an 11% difference in the rate of initial successful hemostasis between the TR Band® arm and either *QuikClot® Radial®* pad arm, a sample size of 100 will be needed for each of the three arms of the trial. Assuming that there may be a 50% screen failure rate (patients withdraw, ulnar access is used, radial access failure, events occur during the procedure that the investigator does not wish to enter the subject or the diagnostic only cases of the study are already filled), a total of up to 600 consecutive subjects undergoing transradial diagnostic cardiac catheterization and/or PCI, who sign informed consent to participate, will be recruited into the three arms of the trial.

An interim analysis was not originally planned for the study, but was conducted after enrolling 186 participants. The results obtained from the interim analysis showed that there was a failure to obtain initial hemostasis at 5 minutes in approximately 30% of the subjects in the QuikClot®/Tegaderm™ arm of the protocol, compared to a failure to obtain initial hemostasis of 11% in the TR Band® cohort (odds ratio = 3.2, 95% CI, 1.2 – 8.1, $p = 0.013$) and a failure to obtain initial hemostasis of 8% in the QuikClot®/Coban™ cohort (odds ratio = 4.7, 95% CI, 1.7 – 12.1, $p = 0.003$). Our DSMB committee reviewed the results and recommended to stop the Tegaderm™ only arm. We here institute a new arm 3 using a QuikClot® Radial® Pad under a TR Band® with 30 minutes of compression to replace the old arm 3 in this trial. The sample size of the new arm 3 is the same as the old arm 3, with 100 participants including 50 diagnostic-only cardiac catheterizations and 50 PCIs.

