Statistical summaries and analyses of data will be performed at Memorial Healthcare System. Descriptive analysis will be performed for all data including means and standard derivation or medians for continuous variables and proportions for categorical variables. The t-test will be used to describe the differences of clinical outcomes between the two compression devices after TRA, and a two-sided p-value of 0.05 will be considered to be statistically significant.

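### The protocol calls the trial adequately powered for safety and efficacy, but only initial hemostasis is powered; at 100 per arm a doubling of RAO from 8% is missed about 58% of the time

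*Combined protocol and SAP*

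**What the plan says.** Section 1.1 (Background) says the two pilots could not settle whether the pad shortens hemostasis, lowers RAO or improves comfort. It then says the investigators for that reason designed a "larger, adequately powered, prospective randomized trial to investigate the safety and efficacy of the" pad. Section 2 (Study Objectives) covers both safety and efficacy, "with the aim to hopefully develop a safe and possibly superior hemostatic method after transradial access".

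Section 7.3 gives one power statement: "power of 80% to detect an 11% difference in the rate of initial successful hemostasis", at 100 per arm. RAO (3.3.1) and access-site complications (3.3.3) are secondary endpoints, with no expected rate, power figure or criterion for interpretation. The inferential method in 7.3 is a t-test for clinical outcomes in general, and "a two-sided p-value of 0.05 will be considered to be statistically significant".

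**The concern.** The argument in 1.1 runs from pilots too small for RAO, among other questions, to a trial large enough for safety and efficacy. A reader would take this to mean that 100 per arm can inform the RAO question. Section 7.3 does not show that, because its calculation concerns another endpoint with a much higher event rate.

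The method adds to the problem. A p-value from a t-test on a rare yes/no outcome shows whether a difference was detected. It does not show how large an excess, or a benefit, remains compatible with the data. At stake is half of the stated objective. A real excess of occlusions could go undetected, and so could the reduction in RAO that 1.1 hopes for.

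**Working it through.** **Inputs from the protocol.** 100 per arm; each pad arm compared with TR Band; two-sided 0.05; t-test (7.3). RAO in up to 8% of transradial patients (1.1), the only RAO rate available as a planning figure. **Assumptions.** Control RAO of 4% and 2%, to show the range below 8%.

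**Step 1: the plan's own figure.** Section 7.3 sets 95% for the pad against 84% for the TR Band. The pooled formula is

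n = [1.96·√(2p̄(1−p̄)) + 0.842·√(p₁(1−p₁)+p₂(1−p₂))]² / (p₁−p₂)²

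With p₁ = 0.84, p₂ = 0.95 and p̄ = 0.895, n = 121 per arm, not 100. Power at 100 per arm is 72% by this formula and 75% by exact enumeration. That gap is a separate point. What matters here is that this is the only power calculation, and it is for hemostasis.

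**Step 2: power for RAO at 100 v 100.** I enumerated every pair of event counts (x, y) with X ~ Bin(100, p_control) and Y ~ Bin(100, p_pad). I applied the two-sample t-test to the 0/1 data and summed the probabilities of pairs with p<0.05 in the true direction.

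| True RAO, TR Band → pad | Power, t-test | Missed, t-test | Missed, Fisher |
|---|---|---|---|
| 8% → 16% | 42.1% | 58% | 66% |
| 8% → 4% | 21.0% | 79% | 86% |
| 4% → 8% (assumed control) | 21.0% | 79% | 86% |
| 2% → 4% (assumed control) | 11.1% | 89% | 96% |

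Hand check of the first row by the normal approximation, with p̄ = 0.12:

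- Null SE = √(2·0.12·0.88/100) = 0.04596.
- Alternative SE = √((0.08·0.92+0.16·0.84)/100) = 0.04561.
- (0.08 − 1.96·0.04596)/0.04561 = −0.22, so power is about 41%.

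Power for a doubling falls as the control rate falls. The statement supported by the protocol's own figure is therefore that a doubling is missed at least about 58% of the time if control RAO is 8% or lower.

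**Step 3: size needed.** The Step 1 formula gives 258 per arm for 80% power at 8% v 16%, and 553 at 4% v 8%.

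**Step 4: what an interval would show.** Newcombe's method combines the two Wilson intervals. With equal counts, the upper bound of the difference is √((u−p)²+(p−l)²).

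- 4/100 in each arm: Wilson 1.57% to 9.84%. √(5.84²+2.43²) = 6.3, so an excess of up to about 6 points is not excluded.
- 8/100 in each arm: Wilson 4.11% to 15.00%. √(7.00²+3.89²) = 8.0, so up to about 8 points.
- 11/100 pad v 4/100 TR Band: difference +7.0 points, 95% CI −0.5 to +15.0, t-test p = 0.06. The result is non-significant, yet the interval reaches a 15-point excess.
- 0/100 in each arm: both variances are zero, so the t statistic is 0/0. The Newcombe interval is still defined, at ±3.7 points.

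**The case against.** By convention, power refers to the primary endpoint, and 7.3 names that endpoint. RAO and complications are labelled secondary, and secondary endpoints are seldom powered. The sentence in 1.1 is background text about the trial's first version and gives no safety power figure. This is fair, and it is why no extra patients are asked for. But the sentence remains in the current protocol, follows directly from a remark about RAO, and the amendment keeps 100 per arm.

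A reader might infer that the investigators will declare the pad safe from p>0.05. No text says so. The 10-per-arm pilot is summarised in 1.4 as having "achieved 100% hemostasis following TRA, with no increased complications noted", but that summary points to a table showing every count. Section 1.5 says the risks of the "pad are the same as for standard of care with TR Band", but this follows a list of risk types and can mean the same kinds of risk. Section 7.3 also promises descriptive proportions, and its interim result is given as odds ratios with 95% CIs, so intervals are within the team's practice. What remains is that nothing in 7.3 commits to intervals for RAO or complications.

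A reader might also extend the miss rates to hematoma. The protocol gives no planning rate for it. By the same t-test, power for a doubling is 52% from 10% and 73% from 15%, so 'usually missed' is not shown there.

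Section 7.3 speaks of two compression devices, which could mean pooling the pad arms. At 200 v 100, power for 8% to 16% is still only about 48%. The sample size text treats the pad arms as two separate comparisons.

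**Conclusion.** The concern holds in a limited form. The adequate-power wording is not supported for RAO and has no calculation behind it for access-site complications. At 100 per arm, a doubling of RAO from 8% is missed about 58% of the time and a halving about 79%. The 79% and 89% figures for a doubling rest on assumed control rates of 4% and 2%; only 'up to 8%' is documented. A non-significant RAO or complication result could not by itself support a claim of safety or of no effect on RAO. The documents do not say that they will make such a claim. The primary analysis is unaffected.

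**What to change.** 1. In 1.1, limit the adequate-power wording to initial successful hemostasis, and say that RAO and access-site complications are not powered. Whether 100 per arm delivers the stated 80% for hemostasis should be handled separately.
2. In 7.3, replace the t-test for RAO and for EASY-graded hematoma/bleeding with the risk difference, each pad arm minus TR Band, and a two-sided 95% Newcombe or Miettinen-Nurminen CI.
3. In 7.3, state that p>0.05 will not be taken as evidence of equal risk, and that the upper bound will be reported as the excess not excluded.

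The cost is a few sentences in 1.1 and 7.3 and one interval per safety endpoint per pad arm, with no added patients, visits or data. The downside is a weaker permitted safety statement: even with equal counts, an excess of about 6 points (4 v 4 events) or 8 points (8 v 8) would remain open.
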